##### *Study Feasibility & Acceptability*

Study feasibility: Study feasibility will be measured by calculating recruitment rates (proportion of enrolled participants to all individuals approached), lost to follow-up (proportion of participants who do not complete post-intervention assessments), relative dose intensity (proportion of completed to planned sessions), early session terminations (proportion of sessions ended by participant prior to completing planned duration), intervention interruptions (missing 3 or more planned sessions consecutively), attendance (proportion of attended to planned sessions), and adherence (gathered from HR/accelerometry data and self-report of exercise via questionnaires). A benchmark to determine feasibility is <40% loss to follow-up.

Intervention acceptability: Acceptability will be measured with qualitative, open-ended to assess participant experience in the intervention and gather information for improving the protocol in future studies. Of particular attention will be the tolerability of a remote, home-based exercise intervention with a semi-supervised format.

Intervention session intensity and adherence: The Rating of Perceived Exertion (RPE) scale asks respondents to rate the intensity of exercise on a 6 – 20 scale. The measure has been validated for estimating both aerobic and resistance exercise exertion levels, providing a standard measure across intervention modalities. Participants will record RPE after each session in order to track session intensity and completion (adherence).

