### **3.0 STUDY AIMS**

1. Determine the feasibility of an individually-adaptive exercise intervention among breast cancer survivors with reduced cardiorespiratory fitness through examination of recruitment rate, enrollment rate, loss to follow-up, intervention adherence, and relative dose intensity (ratio of total completed to total planned cumulative dose)

2. Examine the endpoint of (a) safety; and explore the endpoints of (b) cardiorespiratory fitness; (c) functional capacity; (d) physiologic changes; and (e) patient reported outcomes (PRO) in the intervention vs control arms.
3. Examine the endpoint of (a) safety; and explore the endpoints of (b) cardiorespiratory fitness; (c) functional capacity; (d) physiologic changes; and (e) patient reported outcomes (PRO) in the AE vs RE vs AE+RE intervention arms.

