#### **4.2.3 Other/Exploratory Endpoints**

##### *Cardiorespiratory Fitness*

Maximal exercise capacity: This study's primary outcome is cardiorespiratory fitness (CRF). This is operationalized as maximal exercise capacity, which is ascertained by measuring peak oxygen consumption (VO2 peak) during CPET. All CPETs will be administered by a trained exercise physiologist using the Modified Bruce protocol, an appropriate testing paradigm for people with reduced physical functioning. This procedure will estimate the VO2 (absolute and relative to bodyweight), VCO2, VE/VCO2, BP, HR. Total exercise time as well as workload and peak exercise will be collected as well. Ventilatory and work efficiency/economy will be calculated. Ventilatory threshold will be determined from VO2 – VCO2 plot (V-Slope).

Intervention adherence (accelerometry): Participants will wear 2 devices during the study: (1) a waist-worn actigraph and (2) a wrist-worn FitBit activity monitor (Charge 4, FitBit, San Francisco, CA). The actigraph will be worn for 7-day intervals immediately prior to the baseline and endpoint assessments. In addition, participants will be asked to wear the actigraph 24-hours per day during that 7-day interval with the exception of when engaged in water activities for the duration of their intervention participation. Together, these data will be used to gauge adherence to the exercise intervention. The raw data generated from these devices will be reviewed by a trained accelerometer analyst for quality control and cleaning. Then the analyst will calculate the amount of time (in min/per day) spent in activities of low-, moderate-, and vigorous-activity. Categorization of the level of physical activity will use accepted cutpoints from the literature.

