#### 4.3.4 Data Collection

Clinical and self-report data will be collected at 3 total timepoints: baseline, 12 weeks, 24 weeks.

**Self-reported data:** Participants will be asked to complete baseline questionnaires ascertaining demographic information, health history and current health behaviors. At all timepoints (i.e. baseline, 12-, and 24-Week) participants will be asked to complete self-reported questionnaires on quality of life, physical activity, and fatigue.

**Clinic visits:** In-person clinic visits will take place at baseline and 24-weeks for all participants. All clinic visits will include anthropometric assessment, MRI, supervised 6MWT and CPET. Participants will complete a supervised 6MWT. Study procedures will occur at the University of Washington Medical Center and the Fred Hutchinson Prevention Center. At intervention completion participants will be asked open-ended questions regarding their experience with the study. The responses will be analyzed for themes to improve future study designs.

**Passive Data Collection:** Some data will be remotely collected via wrist- and waist-worn actigraphy monitors, worn in the 7 days prior to each clinic visit. Wrist-worn monitors will be worn 24 hours a day including sleep, while waist-worn monitor will be removed for sleep. Wrist-worn devices will also be utilized during all intervention sessions, as a measure of intervention adherence.

Measure	Type of measure	Instrument	Source
Sample Characteristics			
Demographics	Baseline	Questionnaire	Participant
Physical & mental health history	Baseline	Questionnaire	Participant
Intervention Feasibility			
Intervention Feasibility	Primary outcome	Attendance/Retention	Case Report Form
Intervention Acceptability	Secondary outcome	Questionnaire	Participant
Exercise intervention adherence	Other/Exploratory outcome	Actigraphy Monitor	Participant
Exercise intervention adherence	Secondary outcome	RPE	Participant
Intervention session Intensity	Secondary outcome	RPE	Participant
Safety			
Safety	Secondary outcome	Adverse Events	Case Report Form
Cardiorespiratory Fitness			
VO 2 (maximal exercise capacity)	Other/Exploratory outcome	CPET	Case Report Form
Functional Capacity			
6MWD (submaximal capacity)	Other/Exploratory outcome	6MWT	Case Report Form
1 Repetition Maximum (strength)	Exploratory outcome	1-RM	Case Report Form
Physiologic Changes			
Anthropometrics	Other/Exploratory outcome	Physical exam	Case Report Form

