## 10.0 STATISTICAL CONSIDERATIONS

For objective 1, we will measure the feasibility of our intervention by calculating recruitment rates (% participants enrolled of those approached), enrollment rate (% enrolled of those eligible), lost to follow-up (% who dropped out of those enrolled), intervention discontinuation rate (% of intervention participants who permanently stop the intervention for any reason by Week 24), intervention attendance (% exercise sessions attended), relative dose intensity (% completed sessions), and compliance (based on accelerometry data, self-report of exercise via questionnaires). A benchmark to determine feasibility includes <40% loss to follow-up.

In objective 2, we will start with an analysis of the safety endpoints by calculating the number and percent of adverse events that occurred during the intervention and during the waitlist control period. This analysis will be stratified by the severity of the adverse events, the seriousness of the adverse events, and by the attribution of the adverse events.

The results from above analyses (for Study Aim 1) will be a primary consideration to inform the feasibility and safety of launching a larger scale intervention from the pilot intervention. If both these sets of data provide indications that the study is feasible and safe, then the exploration of additional intervention outcomes will take place. These data will be presented in a manuscript to describe the potential for this intervention. The following analyses will explore additional intervention outcomes to inform the intervention's potential to have an impact on CRF, functional capacity, physiologic changes, and PRO in a larger scale intervention.

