In addition, we will explore potential moderators of the intervention, namely baseline BMI and physical activity, and adherence to the intervention for Objectives 2 and 3, and as guidance in designing the subsequent large-scale intervention. First, we will stratify upon BMI to explore whether the intervention showed greater benefit in those with higher BMI. Then we will repeat this for baseline physical activity to explore whether the intervention showed greater benefit in those with lower baseline physical activity. Next, the level of adherence to the intervention will be evaluated by examining the accelerometry data output in conjunction with the self-reported physical activity data. We will also conduct qualitative analyses utilizing data from the elicitation interviews conducted at the end of the intervention. This analysis will summarize data collected from the participants' into themes.

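### Aim 1 defines relative dose intensity by cumulative dose, but Sections 4.2.2 and 10.0 count sessions, so a participant who completes every session at a reduced level scores 100%

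*Combined protocol and SAP*

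**What the plan says.** Relative dose intensity (RDI) is described in three places. Section 3.0, Aim 1, has "relative dose intensity (ratio of total completed to total planned cumulative dose"). Section 4.2.2, under study feasibility, has "relative dose intensity (proportion of completed to planned sessions"). Section 10.0 has "relative dose intensity (% completed sessions"). The two operational sections agree with each other and differ from the aim. No section gives a unit for dose or says when a session counts as completed.

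The Section 4.2.2 list also contains "attendance (proportion of attended to planned sessions"), a separate measure of sessions ended early, and "adherence (gathered from HR/accelerometry data and self-report of exercise via questionnaires").

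Appendix D sets the exercise dose by level. Aerobic (AE) sessions last 30, 40 and 50 minutes at Levels 1, 2 and 3. Resistance (RE) sessions last 30, 30 and 40 minutes, with twice-weekly sessions at Level 1. Intensity rises with level in both. Footnote 2 prescribes 3 weeks at Level 1, 3 at Level 2 and 6 at Level 3, and allows a move up only when the RPE rating is 13 or lower. Sections 6.1 and 6.1.1 also make progression depend on tolerance.

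**The concern.** A session count can stand in for cumulative dose only if every session carries the same dose, and Appendix D rules that out. A participant who attends faithfully but does not progress receives less than the prescribed exercise, yet her session-based RDI is 100%.

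This matters because Section 10.0 makes the Aim 1 results a main input to the decision on a larger trial. For survivors with reduced fitness, that decision should rest on whether they can reach the prescribed dose as well as on whether they take part. Good attendance with stalled progression would call for a different progression scheme, and the ratio as computed could not show it.

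**Working it through.** The documents give no RDI value or threshold, so there is no figure to reproduce. What follows is arithmetic on the Appendix D schedule.

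**Assumptions.** Weeks 1-12 only; every scheduled session done in full; dose measured in minutes, without warm-up and cool-down; planned dose equal to the 3/3/6-week progression; RE at three sessions a week from Level 2.

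**Planned totals** (weeks at each level × weekly amount):
- AE minutes: 3×90 + 3×120 + 6×150 = 1530. AE sessions: 12×3 = 36.
- RE minutes: 3×60 + 3×90 + 6×120 = 1170. RE sessions: 3×2 + 9×3 = 33.

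**Delivered dose when progression stalls:**

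| Case | Sessions | Minutes |
|---|---|---|
| AE, 3 weeks late leaving Level 2 | 36/36 = 100% | (270+720+450)/1530 = 1440/1530 = 94.1% |
| AE, held at Level 2 from Week 4 | 36/36 = 100% | (270+1080)/1530 = 1350/1530 = 88.2% |
| AE, held at Level 1 throughout | 36/36 = 100% | 12×90/1530 = 1080/1530 = 70.6% |
| RE, 3 weeks late leaving Level 2 | 33/33 = 100% | (180+540+360)/1170 = 1080/1170 = 92.3% |
| RE, held at Level 2 from Week 4 | 33/33 = 100% | (180+810)/1170 = 990/1170 = 84.6% |
| RE, Level 1 at 2 per week (Appendix D) | 24/33 = 72.7% | 12×60/1170 = 720/1170 = 61.5% |
| RE, Level 1 load, 3 per week after Week 3 (Section 6.1) | 33/33 = 100% | 33×30/1170 = 990/1170 = 84.6% |

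**Which cases are plausible.** The Level 2 target RPE is 13-14, so a participant on target at 14 does not qualify to move up. A hold at Level 2 is therefore realistic. The Level 1 target is 12-13, which already meets the rule, so twelve weeks at Level 1 is a remote worst case.

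**Arm averages.** With 30 participants at 2:1 and then 1:1, about 10 start AE (30 × 2/3 × 1/2). If k of them are held at Level 2 from Week 4 and the rest follow the schedule, mean RDI by minutes is ((10−k)×100 + k×88.2)/10. For k = 1, 3 and 5 this gives 98.8%, 96.5% and 94.1%, against 100% by sessions.

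**Relation to attendance.** Both ratios divide by planned sessions, so they differ only through sessions attended but not completed. With no early stops they are equal. With 4 of 36 sessions stopped early, attendance is 100% and session-based RDI is 32/36 = 88.9%.

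**What minutes miss.** The two RE cases with 990 minutes differ in load. Weighting minutes by 50%, 60% and 70% of 1-RM, the plan is 180×0.5 + 270×0.6 + 720×0.7 = 756. A hold at Level 2 gives (90 + 810×0.6)/756 = 76.2%, and Level 1 load throughout gives 990×0.5/756 = 65.5%. Minutes alone cannot separate these two.

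**The case against.** **Aim 1 gives no unit, so sessions may be the intended working definition.** The aim could be a general statement that the later sections make specific, and equating dose with minutes is an assumption of this review. That is fair. But sessions of unequal length and intensity are a poor unit for a cumulative dose, whichever unit was meant.

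**Being held back is part of the protocol.** A participant kept at Level 2 by the RPE rule is following the plan. If the planned dose means the plan as adjusted for tolerance, she scores 100% by minutes too. This stands: the shortfalls above depend on the fixed 3/3/6 denominator, and the documents do not say which denominator applies.

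**Other measures show delivered exercise.** RPE is recorded after each session. Section 4.3.4 (Data Collection) adds: "Wrist-worn devices will also be utilized during all intervention sessions, as a measure of intervention adherence". Section 10.0 says that "the level of adherence to the intervention will be evaluated by examining the accelerometry data output in conjunction with the self-reported physical activity data". The per-protocol analysis requires at least 85% of the required activity. These give a partial view, and heart rate may show under-dosing in AE, where levels are set by heart rate. None is defined as a ratio of completed to planned dose. The stated accelerometry output is minutes per day by activity category; of the waist device, Section 4.2.3 says: "The actigraph will be worn for 7-day intervals immediately prior to the baseline and endpoint assessments". RPE does not reveal the level, and the 85% criterion has no unit.

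**A reader might infer that RDI simply repeats attendance, or that a 30% shortfall would routinely go unseen.** The documents support neither. Sessions stopped early separate RDI from attendance. The 70.6% figure needs RPE to stay above its Level 1 target for twelve weeks although Section 6.1 adjusts intensity from RPE. In RE at two sessions a week, the session count itself falls to 72.7%.

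**Conclusion.** The concern holds in a limited form. The analysis in Sections 4.2.2 and 10.0 does not deliver the quantity named in Aim 1, and it gives 100% to a participant who completes every session at a reduced level. For a hold at Level 2 from Week 4, the gap over Weeks 1-12 is 11.8 percentage points of planned minutes in AE (100 − 88.2) and 15.4 in RE (100 − 84.6). Both figures assume that dose is minutes and that the denominator is the prescribed progression. The number of participants affected is unknown, and the gap in an arm average would be smaller.

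It would be wrong to infer that the pilot's feasibility conclusion is unsound. RDI is one of several descriptive secondary measures and has no benchmark. The primary endpoint, all-cause discontinuation of the intervention, and the benchmark of under 40% loss to follow-up are unaffected. The change should be made, but the trial does not depend on it.

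**What to change.** In Sections 4.2.2 and 10.0:

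1. Keep the present ratio under the name session completion.
2. Define RDI as completed minutes divided by the minutes Appendix D prescribes, with a denominator that is not lowered when a participant is held back. Count a completed session at the Appendix D length for the level delivered, and a session ended early at its actual minutes.
3. Report weeks spent at each level by arm. Minutes miss intensity, and RE Levels 1 and 2 both use 30-minute sessions.
4. Report Weeks 1-12 against the 3/3/6 schedule, and state a separate denominator for Weeks 13-24. The documents do not now fix one. It should cover responders continuing AE or RE, and non-responders moved to AE+RE, for whom the combined column of Appendix D is the natural source.

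The cost is small. Level and minutes must be logged for every session, including the unsupervised ones, which are two of three in most weeks. No section says this is done now, although participants already enter an RPE rating each time. RDI will look less favourable. Fixing the denominator at the prescribed schedule is a design choice, since progression is also by tolerance, so the text should say that it was made deliberately.

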#### *Functional Capacity*

Submaximal exercise capacity: Submaximal exercise capacity, also considered functional capacity, will be determined with the six minute walk test (6MWT), which measures the distance a person can walk in six minutes (6MWD). A widely used measure of submaximal exercise capacity, the 6MWT will be administered at all study timepoints to evaluate intervention response.

Strength: One Repetition Maximum (1-RM) or the maximum amount of force that can be generated in one maximum effort movement, will be used to assess participant strength at each time point. A chest press machine and leg press machine will be utilized to separately estimate upper body strength and lower body strength for each participant. The 1-RM test will be administered by a trained exercise physiologist.

#### **4.2.3 Other/Exploratory Endpoints**

##### *Cardiorespiratory Fitness*

Maximal exercise capacity: This study's primary outcome is cardiorespiratory fitness (CRF). This is operationalized as maximal exercise capacity, which is ascertained by measuring peak oxygen consumption (VO2 peak) during CPET. All CPETs will be administered by a trained exercise physiologist using the Modified Bruce protocol, an appropriate testing paradigm for people with reduced physical functioning. This procedure will estimate the VO2 (absolute and relative to bodyweight), VCO2, VE/VCO2, BP, HR. Total exercise time as well as workload and peak exercise will be collected as well. Ventilatory and work efficiency/economy will be calculated. Ventilatory threshold will be determined from VO2 – VCO2 plot (V-Slope).

Intervention adherence (accelerometry): Participants will wear 2 devices during the study: (1) a waist-worn actigraph and (2) a wrist-worn FitBit activity monitor (Charge 4, FitBit, San Francisco, CA). The actigraph will be worn for 7-day intervals immediately prior to the baseline and endpoint assessments. In addition, participants will be asked to wear the actigraph 24-hours per day during that 7-day interval with the exception of when engaged in water activities for the duration of their intervention participation. Together, these data will be used to gauge adherence to the exercise intervention. The raw data generated from these devices will be reviewed by a trained accelerometer analyst for quality control and cleaning. Then the analyst will calculate the amount of time (in min/per day) spent in activities of low-, moderate-, and vigorous-activity. Categorization of the level of physical activity will use accepted cutpoints from the literature.

#### *Physiologic Changes*

Anthropometrics: Prior to the measurement of body weight, participants will be instructed to remove heavy clothing and empty pockets of their contents. Weight will be measured to the nearest one-tenth kg with a calibrated balance beam or digital scale. Height will be measured while the participant stands without shoes using a wall-mounted stadiometer to the nearest one-tenth cm. Hip and waist circumference will be measured to the nearest one-tenth cm.

Intermuscular fat (IMF): The ratio of thigh IMF to skeletal muscle (SM) will be ascertained via MRI by trained MRI technologists (see Appendix C for the MRI protocol). Participants will undergo a screening process with the MRI technologist to ensure that eligibility criteria for MRI scans are met. Participants will then change into a hospital gown and enter the MRI scanner. In this longitudinal assessment of IMF, the MRI technologist will be instructed to match participant scan positions across time by matching the current scan position with the participant's previous scan position, recorded at the timepoint prior. MRI analysts will quantitate total and compartment amounts of muscle and adipose tissue using cross-sectional areas of thigh skeletal muscle (SM) and IMF using commercially available software. Thigh IMF area will be calculated as the number of fat pixels within the thigh musculature multiplied by the pixel surface area. The analyst will be blinded to MRI visit number, participant's prior/future MRI results, intervention group, and participant characteristics. This technique for determining muscle composition has been validated against cadaver specimens.

Abdominal depots of fat: Subcutaneous (SQ) fat and visceral adipose tissue (VAT) will be assessed via abdominal MRI (see MRI Protocol in Appendix C). For analysis, fat depots will be separated into abdominal SQ fat and VAT which will be further segmented into intraperitoneal (IP) and retroperitoneal (RP) fat using commercially available software. SQ fat will be defined as the fat outside the muscular abdominal wall; IP fat as fat within the mesentery and omentum bounded anteriorly and laterally by the abdominal wall and posteriorly by a curved line drawn between the kidneys; RP fat as the remaining fat. Adipose tissues will be segmented and colored from other tissues based on pixel intensity and known divisions of tissue planes. The MRI analyst, blinded to participant characteristics, will correct any misidentified fat or non-fat regions using manual tools provided within the software. To calculate each of the compartmental fat deposits, the number of subpixels within each fat compartment (SQ, VAT, IP, and RP) will be multiplied by the individual pixel dimensions within the image and by the slice thickness to determine the area of fat (in cm^2) for each compartment.

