### Sample Images

[figure not shown]
**Series Name:** ABD\_FAT (REF B)

**Series Description:** T1 weighted turbo spin-echo sequence acquired with 3 evenly spaced axial slices with 1st and 3rd centered at L2 and L4.

**Notes:** To assess visceral fat, a series of images will be acquired to assess visceral fat volume. Open up field of view (FOV) to encompass all of the abdomen.

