### **Image Parameters**

Image Parameter	Value
FOV	Open to encompass all of the abdomen
Slice Thickness	5mm
Slice Gap	Variable – change distance factor as necessary
TR	800 ms
TE	36 ms
Flip Angle	180 degrees
Matrix	256 * 256
Acceleration factor	2
Bandwidth	305 Hz/Px
Turbo factor	11
Echo trains per slice	13
Gating	ECG triggering

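### The abdominal fat formula multiplies by slice thickness, so its result is a slab volume although it is labelled an area in cm²; a minor correction to an exploratory outcome

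*Combined protocol and SAP*

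**What the plan says.** Section 4.2.3 (Physiologic Changes, abdominal depots of fat) starts from "the number of subpixels within each fat compartment (SQ, VAT, IP, and RP"), and says this count will be "multiplied by the individual pixel dimensions within the image and by the slice thickness to determine the area of fat". The unit given is cm². It does not say whether the slices are summed, averaged or reported one by one.

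The paragraph on intermuscular fat in the same section computes thigh fat area as pixel count times pixel surface area, without a thickness term.

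Appendix C, series ABD_FAT (REF B), describes the abdominal purpose differently: "a series of images will be acquired to assess visceral fat volume". It acquires "3 evenly spaced axial slices with 1 st and 3 rd centered at L2 and L4". The image parameters for that series give a slice thickness of 5 mm and a gap entered as "Variable – change distance factor as necessary".

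Section 10.0 names VAT, SQ, RP and IP fat as outcomes in the baseline to 24-week comparison of intervention with waitlist control. The measures table in Section 4.3.4 (Data Collection) classes abdominal fat as other/exploratory.

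**The concern.** Pixel count times pixel dimensions is already an area. Multiplying by thickness turns it into a volume, so the formula and its unit cannot both be right. The two imaging outcomes also use the word area for different constructions, and the imaging appendix says the abdominal target is a volume.

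Relabelling cm² as cm³ would not settle this. The result would then be the volume of three thin slabs. If the intended quantity is the fat between L2 and L4, the tissue between the slabs is missing. Two analysts who follow the text faithfully could report different quantities.

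What is at stake is the absolute size of four named outcomes. Section 10.0 wants these analyses to inform a larger trial. Means, SDs and differences on a wrong scale cannot be set beside results from other studies.

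**Working it through.** The plan states no fat value or sample size calculation that depends on this formula, so there is no figure to reproduce. The check is one of dimensions and scale.

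**Inputs from the documents**
- Thickness t = 5 mm = 0.5 cm (Appendix C, ABD_FAT image parameters).
- Three evenly spaced slices, the first and third centred at L2 and L4 (Appendix C, ABD_FAT).
- Gap variable, and absent from the formula.

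**Assumptions**
- L2-L4 centre-to-centre distance D: 60-80 mm, with 50-90 mm as a wider range. The documents give no figure.
- Equal fat area A on the three slices, to isolate the effect of spacing.

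**1. Dimensions.** Written rule: Q = N × (px × py) × t, which is length × length × length, a volume. Area: A = N × px × py. Hence Q = A × t.

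**2. Size if area is meant.** For A = 100 cm² on one slice:
- t in cm: Q = 100 × 0.5 = 50, which is 0.5 times the true number.
- t left in mm: Q = 100 × 5 = 500, which is 5 times the true number.

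Pixel size cancels from Q/A, so the field of view does not matter. If the three slices were summed with t in cm, the value would be 3 × 50 = 150, which is 1.5 times the average slice area.

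**3. Effect on comparisons if area is meant.** Thickness is fixed, so the factor is the same for every participant and visit. A fall from 100 to 90 cm² becomes 50 to 45, and both are −10%. Means and SDs scale together, so difference/SD and test statistics do not change.

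**4. Size if L2-L4 volume is meant.** The formula, summed over slices, covers 3 × 5 = 15 mm of tissue. The centre-to-centre volume by the trapezoid rule, with spacing d = D/2, is V = d × (A1/2 + A2 + A3/2). With equal areas this is 2 × d × A = D × A. The shortfall is therefore D/15 mm.

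| Assumed D (mm) | Spacing d (mm) | Gap (mm) | Slab volume, A = 100 cm² (cm³) | L2-L4 volume (cm³) | Shortfall |
|---|---|---|---|---|---|
| 50 | 25 | 20 | 150 | 500 | 3.3-fold |
| 60 | 30 | 25 | 150 | 600 | 4-fold |
| 80 | 40 | 35 | 150 | 800 | 5.3-fold |
| 90 | 45 | 40 | 150 | 900 | 6-fold |

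Because D differs between women, so does the factor.

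**5. Counted element.** The rule counts subpixels but multiplies by pixel dimensions. If the software split each pixel 2 × 2 or 4 × 4 (an assumption), using full pixel dimensions would inflate the result a further 4 or 16 times.

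**The case against.** The best defence is that the product is a legitimate quantity, the volume of the imaged slabs, with a wrong name and unit. Appendix C speaks only of visceral fat volume and does not say that it must be integrated from L2 to L4. This stands. A reader might infer that the formula yields no valid quantity at all, and that goes too far.

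A reader might also infer that the pilot's fat data would be useless for planning the larger trial. The documents do not support that. With fixed thickness and area as the target, a sample size based on difference/SD is unchanged, and true areas can be recovered by dividing by the thickness once its unit and the handling of slices are known. What is lost is the absolute scale.

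A third tempting reading is a 6- to 8-fold volume error, from spacing over thickness (30/5 and 40/5). That rests on sum of areas × spacing, which represents three spacings (90-120 mm), whereas the L2-L4 span is two (60-80 mm). With equal areas it overstates the L2-L4 volume by 50%, so it is neither the right yardstick nor a suitable correction.

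The variable gap is no defect in itself: it lets evenly spaced slices fall on L2 and L4 in people of different size. It matters only if volume is intended.

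Finally, this is a 30-person pilot, the outcome is exploratory, its analysis is conditional on feasibility and safety, and no decision rule uses an absolute fat value. All of that stands and limits the weight of the point. None of it makes the formula an area.

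**Conclusion.** The point holds. The written rule gives a slab volume while the plan calls it an area in cm², and nothing else in the documents corrects it.

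If area is meant, each single-slice value is off by a constant factor: 0.5 with thickness in cm, 5 with thickness in mm. Absolute means, SDs, differences and comparison with other studies are wrong; tests, standardized effects and percent changes are not affected.

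If the fat volume from L2 to L4 is meant, the rule falls short by about 4- to 5.3-fold at an assumed 60-80 mm (3.3- to 6-fold at 50-90 mm), given equal slice areas, and the factor varies between participants.

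The documents do not show which quantity is intended. Since the outcome is exploratory, this is a minor correction.

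**What to change.** Choose one quantity and make Section 4.2.3 and Appendix C (ABD_FAT) agree.

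- **Area**, which matches the thigh method: count × area of the counted element (subpixel or pixel, whichever the software counts), in cm², with no thickness term. State whether the three slices are averaged or reported singly.
- **Volume**: in cm³, centre to centre from L2 to L4, as spacing × (A1/2 + A2 + A3/2). Use the slice spacing (thickness plus gap) recorded at each visit.

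The cost is a change of wording and one line of image processing. The volume option also needs the slice spacing kept on record for each scan. Neither option needs new scans.
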